**Secondary Outcome Measures:**

4. Kinetics of SARS-CoV-2. IgM Nucleocapside

IgM (nucleocapside) ELISA kits (Inmunodiagnostic Limited ©). Positivity thresholds were provided by the assay manufacturers and were considered positive with an index value greater than 1.1, indeterminate from 0.9 to 1.1 and negative if <0.9 index units

[Time Frame: Baseline, 7 days, 15 days, 3, 6, 9 and 12 months after the beginning of the study]

5. Kinetics of SARS-CoV-2. IgG Nucleocapside

IgG (nucleocapside) ELISA kits (Inmunodiagnostic Limited ©). Positivity thresholds were provided by the assay manufacturers and were considered positive with an index value greater than 1.1, indeterminate from 0.9 to 1.1 and negative if <0.9 index units

[Time Frame: Baseline, 7 days, 15 days, 3, 6, 9 and 12 months after the beginning of the study]

6. Kinetics of SARS-CoV-2. IgG Spike

IgG (spike). ELISA kits DECOV1901 (Demeditec Diagnostics GmbH©). Positivity thresholds were provided by the assay manufacturers and were considered positive with an index value greater than 40, indeterminate from 32 to 40 and negative if <32 UI/ml

[Time Frame: Baseline, 7 days, 15 days, 3, 6, 9 and 12 months after the beginning of the study]

7. Kinetics of SARS-CoV-2. T-Cell

SARS-CoV-2 specific CD4+ and CD8+ T-cell responses we performed an IFN $\gamma$  ELISPOT assay. Wells will be considered positive if they contained at least 50 spot-forming cells per 10^6 PBMCs above the background level (2X mean + 3Xstandard deviation).

[Time Frame: Baseline, 7 days, 15 days, 3, 6, 9 and 12 months after the beginning of the study]

8. To assess the relation between clinical variables and initial RT-PCR results in the whole sample and by sex.

To study the differences between clinical spectrums and initial RT-PCR we will use ANOVAs or Kruskal-Wallis tests, after checking normality assumption using a Shapiro-test

[Time Frame: Baseline, to 12 months after the beginning of the study]

9. To analyse the relation between clinical variables and the interindividual differences in the immune response in early, mid, and long periods of immunization in the whole sample and by sex

To study the differences between clinical spectrums and immune response in early period we will use ANOVAs or Kruskal-Wallis tests, after checking normality assumption using a Shapiro-test . Similarly, to look for differences in antibody levels between sex, either a t-test or a Mann-Whitney test will be performed.

[Time Frame: Baseline, 7 days, 15 days, 3, 6, 9 and 12 months after the beginning of the study]

10. Cytokines as biomarkers of disease progression in early, mid, and long periods of immunization.

Cryopreserved plasma samples will be used in a 45-plex assay of soluble mediators. The plates will be read with a Luminex instrument (Luminex 200, Austin Luminex, USA).Appropriate statistical tests (i.e. t-test or Mann-Whitney to compare between sexes and ANOVA or Kruskal-Wallis to compare between clinical spectrums) will be used after checking for normality (Shapiro-test)

[Time Frame: Baseline, 7 days, 15 days, 3, 6, 9 and 12 months after the beginning of the study]

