### 5.2.2 SECONDARY AIM

1. To determine the kinetics of SARS-CoV-2 antibodies and cellular immune response in early, mid, and long periods of immunization.
2. To assess the relation between clinical variables and initial RT-PCR results with the interindividual differences in the immune response in early, mid, and long periods of immunization.
3. To analyze differentially expressed cytokines as biomarkers of disease progression in early, mid, and long periods of immunization.

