#### 6.8.2.2. TO ASSESS THE RELATION BETWEEN CLINICAL VARIABLES AND INITIAL RT-PCR RESULTS WITH THE INTERINDIVIDUAL DIFFERENCES IN THE IMMUNE RESPONSE IN EARLY, MID, AND LONG PERIODS OF IMMUNIZATION.

The incidence by SARS-CoV-2 will be linked to the sociodemographic, epidemiological, clinical and immunological information collected in the project. To analyze this, an exploratory bivariate analysis will be performed using the appropriate bivariate tests. Chi-squared tests will be used to find if there were any significant differences between the expected and the observed frequencies in categorical comparisons (e.g., the prevalence of symptoms per sex or clinical spectrum).. To study the differences between clinical spectrums and initial RT-PCR we will use ANOVAs or Kruskal-Wallis tests, after checking normality assumption using a Shapiro-test . Post-hoc analyses will be performed to find significant differences between clinical spectrum and immune response. Similarly, to look for differences in antibody levels between sex, either a t-test or a Mann-Whitney test will be performed.

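### Secondary aim 2 relates the initial RT-PCR result to the immune response, but no named analysis compares the two

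*Combined protocol and SAP*

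**What the plan says.** Secondary aim 2 in section 5.2.2, repeated in the Abstract and in the heading of section 6.8.2.2, reads "To assess the relation between clinical variables and initial RT-PCR results with the interindividual differences in the immune response". The immune response is the outcome; clinical variables and the initial RT-PCR result are two predictors.

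Section 6.6.2 splits this into two secondary outcomes. Outcome 8 is "To assess the relation between clinical variables and initial RT-PCR results in the whole sample and by sex". Outcome 9 is "To analyse the relation between clinical variables and the interindividual differences in the immune response", and its named tests are by clinical spectrum and by sex.

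Section 6.8.2.2 gives the analyses for the aim. On RT-PCR it says "To study the differences between clinical spectrums and initial RT-PCR we will use ANOVAs or Kruskal-Wallis tests", after a Shapiro check. On the immune response it says "Post-hoc analyses will be performed to find significant differences between clinical spectrum and immune response", and adds a comparison of antibody levels between the sexes. Two general sentences precede these: "The incidence by SARS-CoV-2 will be linked to the sociodemographic, epidemiological, clinical and immunological information collected in the project", and "Chi-squared tests will be used to find if there were any significant differences between the expected and the observed frequencies in categorical comparisons".

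Section 6.6, under laboratory assays, presents RT-PCR as a diagnostic test run on a real-time assay with four gene targets. The documents define no cycle-threshold (Ct) or viral-load variable.

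**The concern.** The aim has two legs: clinical variables against immune response, and initial RT-PCR against immune response. The outcomes carry the first leg forward and put a different pairing, clinical variables against RT-PCR, in place of the second. A team that follows the plan will report RT-PCR by severity. It will not report whether the initial virological result goes with higher or lower antibody, T-cell or cytokine levels, although the aim says that it will.

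If the gap is noticed only at analysis, the comparison will be improvised. That is risky here, because the way RT-PCR-negative people enter the infected cohort and are sampled makes an unplanned contrast easy to misread.

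**Working it through.** **Step 1. Every named analysis, by what it pairs.**

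| Place | Pairing |
|---|---|
| 6.6.2, outcomes 4 to 7 | antibody and T-cell measures over time |
| 6.6.2, outcome 8 | clinical variables with RT-PCR |
| 6.6.2, outcome 9 | clinical spectrum and sex with immune response |
| 6.6.2, outcome 10, and 6.8.2.3 | clinical spectrum and sex with cytokines |
| 6.8.1 | healthy and infected cohorts on all information, including immunological |
| 6.8.2.1, LOESS | antibodies over time, by clinical condition or gender |
| 6.8.2.1, NLME | antibodies over time, by clinical spectrum and sex |
| 6.8.2.2 | spectrum with RT-PCR; spectrum with immune response; sex with antibodies |

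None pairs initial RT-PCR with an immune measure. The cohort comparison in 6.8.1 is no substitute: section 6.5 defines the infected cohort by RT-PCR, serology or both, so it can hold RT-PCR positives and negatives together.

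**Step 2. Does the plan's power figure cover the missing comparison?** Inputs from section 6.4: two groups, eta squared 0.01, alpha 0.05, power 90%.

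- f² = 0.01 / (1 − 0.01) = 0.0101, a standardised difference of 2 × √0.0101 = 0.201.
- Noncentral F: the smallest n is 522 per group, with power 0.9005. The plan's figure reproduces, and so does its dropout inflation: 522 / 0.9 = 580.

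That calculation is for two equal groups. RT-PCR positives and negatives within the infected cohort need not be equal, and the documents give no share. Assume a share s of 675 is negative, so n₂ = 675s and n₁ = 675 − n₂. The detectable difference at 90% power is (1.960 + 1.282) × √(1/n₁ + 1/n₂).

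| Assumed share negative | Detectable difference (SD) | Power for 0.201 SD |
|---|---|---|
| 5% | 0.57 | 21% |
| 10% | 0.42 | 35% |
| 20% | 0.31 | 55% |
| 50% | 0.25 | 74% |

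**Step 3. Does the choice of test for outcome 8 matter?** On a positive/negative variable, tie-corrected Kruskal-Wallis equals Pearson chi-squared × (N − 1)/N. With an invented table of 60/40, 300/175 and 80/20 (N = 675), the Shapiro test rejects in each group, so the plan's rule leads to Kruskal-Wallis: H = 11.716 × 674/675 = 11.699, p = 0.00288, against p = 0.00286 for chi-squared. The choice changes no conclusion.

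**Step 4. What would distort an improvised comparison?**

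- Entry: under section 6.5, a person with negative RT-PCR is classed as infected because antibodies are positive. A baseline antibody contrast by RT-PCR result is therefore partly fixed by the cohort definition.
- Sampling: in Tables 2 and 5, at visits 5 and 6, the RT-PCR-positive infected group (in Table 2, the recently infected) all have T-cell and cytokine assays. The RT-PCR-negative infected group has them only if antibodies were present at Visit 4. A plain contrast would set unselected positives against antibody-selected negatives.

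**The case against.** The best case against the point is that the link is vague but present. Section 6.7 lists RT-PCR among the laboratory results held with clinical variables in the primary care record, so outcome 9 might be read to include it. Section 6.6.2 opens with a general intention to relate prognostic factors to immune response. Section 6.8.2.2 promises to link incidence to immunological information.

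This does not close the gap. Aim 2 and outcome 8 both name RT-PCR alongside clinical variables, as something distinct from them. The named tests in outcome 9 stop at spectrum and sex. The incidence sentence names neither the initial RT-PCR result nor an immune endpoint, and leaves the test open.

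Three parts of the opposing case do stand.

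- A reader might infer that the study cannot answer this half of the aim. The documents do not support that: RT-PCR and immune measures are both collected, and Tables 2 and 5 already separate infected participants by RT-PCR result.
- A reader might infer that ANOVA or Kruskal-Wallis for RT-PCR is a serious error. Step 3 shows that it is harmless for a positive/negative result, and the tests would suit a quantitative readout. The plan does not say which form is meant, so the variable needs defining.
- This is half of one secondary aim, and section 6.8.2.2 calls its bivariate work exploratory. The primary aim is untouched.

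**Conclusion.** The point holds, at moderate severity. Aim 2 promises a comparison of immune response by initial RT-PCR result; the outcomes and the analysis sections name none and put RT-PCR by clinical spectrum in its place. This conclusion rests only on reading the sections side by side.

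The power range of 21% to 74% shows that the 522-per-group calculation does not speak to this comparison. It rests on the assumed 5% to 50% share of RT-PCR negatives, on 675 infected participants with no dropout, and on a two-group comparison without covariates. It does not show that the study is underpowered for its stated design.

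**What to change.** 1. Keep outcome 8 as a descriptive table of clinical spectrum by RT-PCR, with chi-squared if the result is positive/negative. Define the RT-PCR variable, and say whether the initial result means Visit 1 or an earlier swab, since Tables 2 and 5 use both.
2. Add to section 6.8.2.2 a regression, within the infected cohort, of each log immune measure in each period on the initial RT-PCR result. Adjust for sex and for time from diagnosis (or from onset, where there is one) to the blood sample. Report it with and without clinical spectrum, which may lie between infection and response.
3. Use Ct among RT-PCR positives where the laboratory recorded it; this avoids the entry selection. Otherwise use positive/negative. The documents do not mention Ct, so its availability must be checked first.
4. State that RT-PCR-negative infected members entered through positive antibodies, so the baseline positive/negative antibody contrast is descriptive only. Limit T-cell and cytokine contrasts at visits 5 and 6 to participants with antibodies at Visit 4 in both RT-PCR groups; the result then applies to antibody-positive participants only.
5. Label the analysis exploratory, with false-discovery-rate control across the cytokine panel. Three antibodies, one T-cell measure and 45 soluble mediators over three periods make (3 + 1 + 45) × 3 = 147 fits. For the panel alone, 45 × 0.05 = 2.25 nominally significant results per period are expected if there is no association.

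If the sponsor does not want this comparison, reword aim 2 to match outcomes 8 and 9.

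The cost is some SAP wording and added analysis work on data already collected. Ct will be missing for tests run elsewhere.

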##### *Sample Size Estimation*

In a one-way ANOVA study, sample sizes of 522, and 522 are obtained from the 2 groups whose means are to be compared. The total sample of 1044 subjects achieves 90% power to detect differences among the means versus the alternative of equal means using an F test with a 0.05 significance level. The size of the variation in the means is represented by the effect size  $\eta^2 = \sigma_m^2 / (\sigma_m^2 + \sigma^2)$ , which is 0.01 [10-13]

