##### *Dropout-Inflated Sample Size*

Average Group Sample Size n	Group	Dropout Rate	Sample Size Ni	Dropout-Inflated Enrollment Sample Size Ni'	Expected Number of Dropouts Di
522	1-2	10%	522	580	58
	Total		1044	1160	116

Average Group Sample Size n	Group	Dropout Rate	Sample Size Ni	Dropout-Inflated Enrollment Sample Size Ni'	Expected Number of Dropouts Di
522,00	1 - 2	10%	522	580	58
	Total		1044	1160	116

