##### NONLINEAR MIXED-EFFECTS (NLME) MODELS

Mixed-effects models are generally useful when there are multiple measures per participant, as in this study. Random effects are included in the model to test if they may be causing any significant, and generally unexpected, significant influence in the modelling built by the fixed effects. Therefore, introducing random effects in the model help to control unobserved variance.

We will use NLME models to study possible differences in the dynamics (kinetics) of SARS-CoV-2 antibodies (IgM, IgG) levels since symptoms onset. After fitting a general model, the differences will be studied between clinical spectrums and biological sex, setting the largest group as reference groups for modelling. To fit these models, we will use all the data available except for those from participants who never tested positive. Time after diagnosis was discretized as follows: Tests made in the first 14 days since diagnosis are treated as "Day 15". Tests from days 15 to 29, as "Day 30", days 30 to 59 as "Day 60", days 60 to 89 as "Day 90", days 90 to 179 as "Day 180", days 180 to 269 as "Day 270", days 270 to 360 as "Day 360", and days 360 up to end of follow-up as "Day 450". However, antibody values beyond 450 days after diagnosis were not considered, as they were only available for 14 participants.

The general equations to be fitted will be:

$$IgM(t) = b_1 + (b_0 - b_1)e^{-k_1 t} - b_1 k_1 (e^{-k_1 t} - e^{-k_2 t})$$

$$IgG(t) = b_1 + (b_0 - b_1)e^{-k_1 t} - b_1 k_1 (e^{-k_1 t} - e^{-k_2 t})$$

Having  $t$  normalized per the maximum number of days (360). This general equation corresponds to an equation describing an exponential rise followed by an exponential decay.  $b_0$  corresponds to the baseline value,  $b_1$  corresponds to the asymptotic value (i.e., antibody levels at  $t \rightarrow \infty$ ),  $k_1$  corresponds to the rise rate, and  $k_2$  to the decay rate.

Nonlinear mixed-effects models will be built using the nlme package [14].

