#### 6.8.2.3. TO ANALYZE DIFFERENTIALLY EXPRESSED CYTOKINES AS BIOMARKERS OF DISEASE PROGRESSION IN EARLY, MID, AND LONG PERIODS OF IMMUNIZATION

Cytokine levels will be studied and compared between different clinical spectrum or sexes to determine their role as a biomarker of disease type. Appropriate statistical tests (i.e. t-test or Mann-Whitney to compare between sexes and ANOVA or Kruskal-Wallis to compare between clinical spectrums) will be used after checking for normality (Shapiro-test). Significance level will be set to 0.05. All the analyses will be performed using R version 3.6.3 or higher.

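### Outcomes 9 and 10 name independent-sample tests by period without fixing one value per worker; entering repeated samples directly would raise type I error above 0.05

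*Combined protocol and SAP*

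**What the plan says.** Section 6.6.2, outcome 9, concerns individual differences in immune response over three periods. Its test sentence reads "To study the differences between clinical spectrums and immune response in early period we will use ANOVAs or Kruskal-Wallis tests", after a Shapiro check, with a t-test or Mann-Whitney test for sex. That sentence names only the early period. The time frame is "Time Frame: Baseline, 7 days, 15 days, 3, 6, 9 and 12 months after the beginning of the study". Outcome 10 has the same time frame and applies the same family of tests to a 45-plex cytokine panel.

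Sections 6.8.2.2 and 6.8.2.3 repeat these tests for all three periods; the latter adds "Significance level will be set to 0.05". None of these places sets day limits for the periods or says which value per worker enters a test.

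Section 6.8.2.1 does recognise the data structure: "Mixed-effects models are generally useful when there are multiple measures per participant, as in this study". Its mixed models are for IgM and IgG levels, including differences by spectrum and sex. No such model is planned for T-cells or cytokines.

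Table 5 schedules T-cells and cytokines for RT-PCR-positive infected workers at visits 1 and 4 to 9, which is seven visits.

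**The concern.** ANOVA, Kruskal-Wallis, t and Mann-Whitney tests take their null distribution from independent observations. Two or three samples from one worker are correlated, so entering them all counts the same person more than once and makes the between-group comparison look more precise than it is. Workers with more samples in a period would also carry more weight.

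An analyst could enter every sample in a period, pick one, or average them, and each choice would comply with the text. The first does not hold its nominal level. Hypotheses 1 to 3 in section 5.1 concern response by clinical spectrum, by sex and other variables, and cytokines as biomarkers, which are the questions these tests address. For T-cells and cytokines there is no model-based analysis to fall back on.

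**Working it through.** **1. The plan's own figure.** Section 6.4 states that "sample sizes of 522, and 522 are obtained from the 2 groups whose means are to be compared", with effect size 0.01, and that "The total sample of 1044 subjects achieves 90% power to detect differences among the means", "using an F test with a 0.05 significance level".
- f² = 0.01/(1 − 0.01) = 0.0101, and the noncentrality is 1044 × 0.0101 ≈ 10.5.
- The noncentral F distribution gives n = 522 per group, power 0.9005. The stated figure reproduces.
- The 10% dropout inflation gives 522/0.90 = 580 per group, also as stated.
- This calculation has two groups and one value per person. It is not affected by the point made here.

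**2. Samples per period.** Seven sampling times over three periods: 7/3 = 2.33, so at least one period holds three or more times if all are assigned. The same count applies to the seven T-cell and cytokine visits in Table 5. The tables give no days. If visits 8 and 9 fell after 12 months (an assumption), five visits would remain, and 5/3 = 1.67 still puts at least two in one period.

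**3. Type I error if samples are entered directly.** Let m be samples per worker in the period and ICC the within-worker correlation. Neither is in the documents; I take m = 1 to 3 and ICC = 0.3 to 0.8.
- The between-group statistic is inflated by DE = 1 + (m − 1) × ICC.
- Three spectrum groups (2 df): α = P(χ²₂ > 5.991/DE) = exp(−5.991/(2 × DE)).
- Two sexes (1 df): α = P(χ²₁ > 3.841/DE).
- Example, m = 3 and ICC = 0.5: DE = 2.0 and exp(−5.991/4) = 0.224.

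| m | ICC | DE | three groups | two groups |
|---|---|---|---|---|
| 1 | any | 1.0 | 0.050 | 0.050 |
| 2 | 0.3 | 1.3 | 0.100 | 0.086 |
| 2 | 0.5 | 1.5 | 0.136 | 0.110 |
| 2 | 0.8 | 1.8 | 0.189 | 0.144 |
| 3 | 0.3 | 1.6 | 0.154 | 0.121 |
| 3 | 0.5 | 2.0 | 0.224 | 0.166 |
| 3 | 0.8 | 2.6 | 0.316 | 0.224 |

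**4. Simulation check.** 675 infected workers, an assumed 20/70/10 severity split (135/472/68), no true difference, 2000 to 3000 runs per setting. Results are ANOVA / Kruskal-Wallis.
- m = 2, ICC 0.5: 0.135 / 0.134.
- m = 3, ICC 0.8: 0.317 / 0.304.
- Only 30% of workers with three samples, the rest with one: 0.139 / 0.132 at ICC 0.5; 0.215 / 0.201 at ICC 0.8.
- m = 3, ICC 0.8, common rise of 1 SD per visit: 0.145 / 0.125. With 0.5 SD per visit: 0.256 / 0.247.
- Worker mean of three samples, ICC 0.8: 0.050 / 0.050.
- One sample per worker: 0.059 / 0.059. The simulation standard error is √(0.05 × 0.95/3000) = 0.004, so this is about two standard errors above 0.05. The F test is exact for independent normal data, so I read the excess as simulation noise.

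**The case against.** The strongest reply is that the plan never says samples are pooled. Under the primary aim (6.6.2 and 6.8.1) it compares cohorts separately at each time point with the same tests, so one value per worker per test is an available reading, and under it there is no inflation. That stands as a limit on the claim. It does not settle the matter, because that wording covers the healthy-versus-infected comparison, whereas outcomes 9 and 10 are framed by period.

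The second reply concerns the early period. It is tempting to assume three early samples for everyone (baseline, day 7, day 15). The visit tables do not support this. Visit 2 is a telephone call for recently infected workers, and non-recently infected workers have no visit at visits 1 to 3 in Table 2. If visits 1 to 3 are those three times, recently infected workers have at most two early antibody samples. In Table 5 infected workers then have one early T-cell and cytokine sample, since the next comes at visit 4. This stands for the early period. It moves the repeats to later periods without removing them.

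Third, antibody differences by spectrum and sex also have a mixed-model analysis in 6.8.2.1, and 6.8.2.2 calls its bivariate work exploratory. Both lower the stakes for antibodies. Neither helps T-cells or cytokines.

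**Conclusion.** The point holds in conditional form. The plan names tests that are invalid for repeated samples if applied to them directly, and contains no rule that prevents this. If every sample in a period were entered, the three-group type I error would be about 0.10-0.19 with two samples per worker and 0.15-0.32 with three, against a nominal 0.05. The sex tests would reach about 0.09-0.14 and 0.12-0.22. These figures rest on an assumed ICC of 0.3 to 0.8 and complete repeat sampling; unequal sampling or a strong common time trend lowers them.

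A reader might infer that the plan pools its samples and will therefore reject three to six times too often. The documents do not support that: pooling is not stated, neither the ICC nor the samples per worker is given, and over the range examined the factor runs from 1.0 (one value per worker) to 6.3 (0.316/0.05). The analyses are secondary, so the change is advisable but does not undermine the study's sample size or primary aim.

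**What to change.** In outcomes 9 and 10 and in sections 6.8.2.2 and 6.8.2.3:

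1. Define early, mid and long by days since diagnosis, and state which Table 5 visits fall in each.
2. Replace the period tests, above all for T-cells and cytokines, with a linear mixed model on a suitable scale (for example log). It should have spectrum or sex as a fixed effect, a term for sampling day, and a random intercept per worker.
3. If the named tests are preferred, state that each uses one value per worker per period, chosen by a rule fixed in advance, such as the sample nearest a set day.

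The mixed model uses all samples and adjusts for sampling day; the single-value rule is simpler but discards data. Either needs a sentence or two per section and no new data. The cost is slightly more analysis work and some less favourable p-values.
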